#### **9.6.4 Safety Analysis**

All AEs, vital signs, ECGs, pulse oximetry, and clinical safety laboratory values will be listed for each participant and tabulated by population. Summary statistics for the clinical safety laboratory tests, vital signs, and/or ECGs may also be computed and provided, as deemed clinically appropriate.

#### **9.7 Interim Analyses**

Not applicable.

#### **9.8 Multiplicity**

Not applicable.

#### **9.9 Sample Size and Power Calculations**

The sample size selected to evaluate the effect of renal impairment on the PK of MK-6482 was not chosen to satisfy any a priori statistical requirement. This sample size (N=6 per group) has historically been shown to be sufficient for studies of this type and should provide adequate data to support the planned analyses. Nevertheless, estimates of the expected precision of the estimates, based on these sample sizes and the known variability obtained from renal PK studies are presented below.

The precision of the estimated GMRs (ESRD before or after HD / normal renal function) of PK parameters obtained from this study can be assessed by calculating the half-width of the

90% CIs expected for the given sample size and assumed variability. The observed between-participant coefficients of variation were 62.44% (~0.574 standard deviation on the log scale) and 56.29% (~0.525 standard deviation on the log scale) for AUC0-inf from food-effect study (Protocol MK-6482-002) and comparative bioavailability study (Protocol MK-6482-006), respectively. Assuming a sample size of 6 participants per population and observed between-participant SD is 0.574 on the log scale, then the half width of the 90% CI of GMR for MK-6482 AUC0-inf on the log scale will be 0.545. The lower and upper 90% confidence limits for the GMR will be given by OBS/1.72 and OBS\*1.72 for AUC0-inf, where OBS is the observed GMR. Thus, for example, if the observed GMR for AUC0-inf was 1.50, then the approximate 90% CI for the GMR would be [0.87, 2.59].

Similarly, the observed between-participant coefficients of variation were 26.04% (~0.256 SD on the log scale) and 25.25% (~0.249 SD on the log scale) for Cmax from Protocol MK-6482-002 and Protocol MK-6482-006, respectively. Assuming a sample size of 6 participants per population and observed between-participant SD is 0.256 on the log scale, then the half width of the 90% CI of GMR for MK-6482 Cmax on the log scale will be 0.243. The lower and upper 90% confidence limits for the GMR will be given by OBS/1.28 and OBS\*1.28 for Cmax. Thus, for example, if the observed GMR for Cmax was 1.50, then the approximate 90% CI for the GMR would be [1.18, 1.91].

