## 9.6.3 PK Statistical Analysis

Separately for each PK parameter, individual values of MK-6482 AUC0-inf, AUC0-24, and Cmax will be natural log-transformed and evaluated with a linear mixed effects model containing a fixed effect for population (participants with ESRD before and after HD, control participants with normal renal function). An unstructured covariance matrix will be used to allow for unequal population variances and to model the correlation between repeated

measures (before and after HD) within each ESRD participant via the REPEATED and SUBJECT statement in SAS PROC MIXED. Kenward and Roger's method will be used to calculate the denominator degrees of freedom for the fixed effect (DDFM=KR). Ninety percent (90%) CIs for the least squares means for each population will be constructed on the natural log scale and will reference the t-distribution. Exponentiating the least-squares means and their corresponding 90% confidence limits will yield estimates for the population geometric means and confidence intervals about the geometric means on the original scale. Sample SAS code is given below:

```
proc mixed data=data;
  class population subject;
  model lnPk = population /ddf=kr;
  repeated population/ subject=subject type=UN;
  lsmeans population /cl alpha=0.10;
  lsmeans population/pdiff alpha=0.10;
  run;
```

To address the primary estimation objective and compare participants with ESRD before and after HD to participants with normal renal function, a two sided 90% CI for the difference in least-squares means (ESRD before HD – normal renal function, ESRD after HD – normal renal function) will be calculated for each PK parameter using the aforementioned model. These confidence limits will be exponentiated to obtain the 90% CI for the ratio of geometric means (ESRD before HD/normal renal function, ESRD after HD/normal renal function) for each PK parameter. The same approach will be used to address the secondary estimation objective. The extent to which MK-6482 is removed from plasma by HD will be evaluated with the difference in means (ESRD before HD – ESRD after HD), the geometric mean ratio (ESRD before HD/ESRD after HD) and their 90% CIs. A sensitivity analysis may be performed without PMs at UGT2B17 or CYP2C19 if applicable as deemed clinically appropriate.

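### The 90% CI half-widths in Section 9.9 use the normal quantile, but the planned analysis uses a t-distribution with about 10 degrees of freedom at most, so precision is overstated by at least 10% on the log scale

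*Combined protocol and SAP*

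**What the plan says.** Section 9.9 explains that the sample size was not set by a formal statistical requirement and rests on historical experience with studies of this type. It then gives the expected precision of the GMR of ESRD (before or after HD) to normal renal function.

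- AUC0-inf: "Assuming a sample size of 6 participants per population and observed between-participant SD is 0.574 on the log scale", the plan concludes that "the half width of the 90% CI of GMR for MK-6482 AUC0-inf on the log scale will be 0.545". It converts this to a multiplicative factor of 1.72 and an interval of [0.87, 2.59] for an observed GMR of 1.50.
- Cmax: with an SD of 0.256, "the half width of the 90% CI of GMR for MK-6482 Cmax on the log scale will be 0.243". The factor is 1.28 and the example interval is [1.18, 1.91].

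The section does not say which quantile was used.

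Section 9.6.3 describes the analysis. Log-transformed parameters go into a mixed model with an unstructured covariance matrix, which lets variances differ between populations, and with Kenward-Roger denominator degrees of freedom. Intervals for the least-squares means "will be constructed on the natural log scale and will reference the t-distribution". For the comparison with normal renal function, "a two sided 90% CI for the difference in least-squares means" is taken from the same model.

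**The concern.** The two sections describe different intervals. The half-widths in Section 9.9 can be reproduced only with a large-sample normal quantile. The analysis in Section 9.6.3 estimates its variances from 6 participants per group and pays for that through the t-distribution.

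This is an estimation study with no hypothesis test and no power figure. The width of the confidence interval is therefore its only numerical measure of adequacy, and the six figures in Section 9.9 are what a reader would use to judge whether 6 per group is informative. All six look more favourable than the planned method gives at the stated SDs.

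**Working it through.** **Inputs**

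- Two-sided 90% interval, so 5% in each tail (Section 9.6.3).
- 6 participants per population (Section 9.9).
- Log-scale SDs from the CVs in Section 9.9: √ln(1 + 0.6244²) = 0.574 for AUC0-inf and √ln(1 + 0.2604²) = 0.256 for Cmax. Both agree with the plan.

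**Formula.** Half-width = quantile × SD × √(1/6 + 1/6), with √(2/6) = 0.57735.

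**Step 1: reproduce the plan's figures with the normal quantile, 1.6449**

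- AUC0-inf: 1.6449 × 0.574 × 0.57735 = 0.5451; exp(0.5451) = 1.72; 1.50/1.7248 = 0.87 and 1.50 × 1.7248 = 2.59.
- Cmax: 1.6449 × 0.256 × 0.57735 = 0.2431; exp(0.2431) = 1.28; 1.50/1.2752 = 1.18 and 1.50 × 1.2752 = 1.91.

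All six stated figures are recovered. No t quantile between 5 and 10 degrees of freedom gives 0.545 or 0.243.

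**Step 2: degrees of freedom under the planned model.** For 6 versus 6 with separate variances, the degrees of freedom are 6 + 6 − 2 = 10 when the two observed variances are equal. They fall towards 5 as one variance comes to dominate.

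**Step 3: recompute with t**

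| | Plan (z = 1.645) | t, 10 df (1.8125) | t, 5 df (2.0150) |
|---|---|---|---|
| AUC0-inf half-width | 0.545 | 0.601 | 0.668 |
| AUC0-inf factor | 1.72 | 1.82 | 1.95 |
| AUC0-inf interval at GMR 1.50 | [0.87, 2.59] | [0.82, 2.73] | [0.77, 2.92] |
| Cmax half-width | 0.243 | 0.268 | 0.298 |
| Cmax factor | 1.28 | 1.31 | 1.35 |
| Cmax interval at GMR 1.50 | [1.18, 1.91] | [1.15, 1.96] | [1.11, 2.02] |

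The log half-width grows by 1.8125/1.6449 = 1.102, or 10.2%, at 10 df, and by 22.5% at 5 df. The 5 df column keeps the same standard error and is a limiting case.

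**Step 4: let the observed SDs vary.** I simulated 400,000 trials of 6 versus 6 with a true SD of 0.574 in both groups, with Satterthwaite degrees of freedom standing in for Kenward-Roger. The median df was 9.1. The mean half-width was 0.596 and the median 0.590 for AUC0-inf. For Cmax (true SD 0.256) they were 0.266 and 0.263. The typical planned interval is thus wider than stated even when the SD is not held at its assumed value.

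**Step 5: coverage.** An interval built from 1.645 and an SD estimated on 10 df would cover 86.9%, since P(|t₁₀| < 1.645) = 0.869. On 5 df it would cover 83.9%.

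**The case against.** The strongest reply is that these are planning figures. N was not derived from them, the example intervals are called approximate, and no conclusion changes: at a GMR of 1.50 the AUC0-inf interval includes 1 and the Cmax interval excludes 1 under either quantile. All of that is true and is why the point is moderate. But the half-widths are quoted to three decimals as what will be obtained, and only the worked examples carry the word approximate.

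A second reply treats 0.574 as the true SD. A fixed ±0.545 interval would then cover 90%, and realised half-widths would vary. In the simulation about 37% fall below 0.545 and about 53% below 0.601. This stands as a limit on wording: 0.601 is the smallest half-width when the observed SD is 0.574 in both groups, not a floor for every possible dataset. The 86.9% figure likewise applies to a z interval with an estimated SD, which the plan does not construct. However, Section 9.9 says observed SD, and the simulated mean is still 0.596.

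Third, the 5 df column is extreme. With the standard error unchanged, it needs one group's SD near 0.574 × √2 = 0.81 and the other's near zero. If one SD stayed at 0.574 and the other fell to zero, the half-width would be 2.015 × 0.574/√6 = 0.472. With equal true variances, df fell below 6 in only about 2.5% of runs. That column is a bound, not an expectation.

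Fourth, the plan used the larger of its two source SDs. With 0.525 for AUC0-inf, t on 10 df gives 0.549, close to the stated 0.545. With 0.249 for Cmax it gives 0.261, still above 0.243. This shows that the error is comparable to the spread between the source studies for AUC0-inf. It does not make the stated calculation right for the SD it names.

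Fifth, Sections 4.1 and 5 allow a 7th ESRD participant. With 7 versus 6 and 11 df the AUC0-inf half-width is 1.7959 × 0.574 × √(1/7 + 1/6) = 0.574, still above 0.545.

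Finally, the explicit reference to the t-distribution is worded for the least-squares means. For the differences it follows from using the same model with Kenward-Roger degrees of freedom.

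**Conclusion.** The concern holds. The half-widths in Section 9.9 rest on the normal quantile, and the analysis in Section 9.6.3 is t-based. At the plan's own SDs, 6 per group and equal observed variances (10 df), the log half-widths are 0.601 instead of 0.545 for AUC0-inf and 0.268 instead of 0.243 for Cmax, about 10% larger. Unequal observed variances with the same average widen them further, up to a limit of 22.5%. The correction should be made, but it does not affect the sample size, the planned analysis or the direction of either worked example.

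**What to change.** Restate Section 9.9 with the t quantile on 10 df:

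- AUC0-inf: half-width 0.601, limits OBS/1.82 to OBS × 1.82, example interval [0.82, 2.73].
- Cmax: half-width 0.268, limits OBS/1.31 to OBS × 1.31, example interval [1.15, 1.96].

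Add a sentence saying that these assume equal observed variances, and that unequal variances lower the degrees of freedom and widen the intervals for the same average variance. If the 5 df values are shown, label them as a limiting case. A weaker alternative is to keep the present figures, state that they use the normal quantile, and warn that the analysis intervals are expected to be wider.

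The cost is a text correction to six figures. N stays at 6 per group, and the stated precision becomes slightly less favourable.

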## 10 SUPPORTING DOCUMENTATION AND OPERATIONAL CONSIDERATIONS

### 10.1 Appendix 1: Regulatory, Ethical, and Study Oversight Considerations

#### 10.1.1 Code of Conduct for Clinical Trials

**Merck Sharp & Dohme LLC, Rahway, NJ, USA (MSD)**

**Code of Conduct for Interventional Clinical Trials**

#### **I. Introduction**

##### **A. Purpose**

MSD, through its subsidiaries, conducts clinical trials worldwide to evaluate the safety and effectiveness of our products. As such, we are committed to designing, implementing, conducting, analyzing, and reporting these trials in compliance with the highest ethical and scientific standards. Protection of participants in clinical trials is the overriding concern in the design and conduct of clinical trials. In all cases, MSD clinical trials will be conducted in compliance with local and/or national regulations (including all applicable data protection laws and regulations), and International Council for Harmonisation Good Clinical Practice (ICH-GCP), and also in accordance with the ethical principles that have their origin in the Declaration of Helsinki.

##### **B. Scope**

Highest ethical and scientific standards shall be endorsed for all clinical interventional investigations sponsored by MSD irrespective of the party (parties) employed for their execution (eg, contract research organizations, collaborative research efforts). This Code is not intended to apply to trials that are observational in nature, or which are retrospective. Further, this Code does not apply to investigator-initiated trials, which are not under the full control of MSD.

#### **II. Scientific Issues**

##### **A. Trial Conduct**

###### **1. Trial Design**

Except for pilot or estimation trials, clinical trial protocols will be hypothesis-driven to assess safety, efficacy and/or pharmacokinetic or pharmacodynamic indices of MSD or comparator products. Alternatively, MSD may conduct outcomes research trials, trials to assess or validate various endpoint measures, or trials to determine patient preferences, etc.

The design (ie, participant population, duration, statistical power) must be adequate to address the specific purpose of the trial and shall respect the data protection rights of all participants, trial site staff and, where applicable, third parties. All trial protocols are and will be assessed for the need and capability to enroll underrepresented groups. Participants must meet protocol entry criteria to be enrolled in the trial.

###### **2. Site Selection**

MSD's clinical trials are conducted globally in many different countries and in diverse populations, including people of varying age, race, ethnicity, gender, and accounting for other potential disease related factors. MSD selects investigative sites based on medical expertise, access to appropriate participants, adequacy of facilities and staff, previous performance in clinical trials, as well as budgetary considerations. Prior to trial initiation, sites are evaluated by MSD personnel (or individuals acting on behalf of MSD) to assess the ability to successfully conduct the trial.

Where appropriate, and in accordance with regulatory authority guidance, MSD will make concerted efforts to raise awareness of clinical trial opportunities in various communities. MSD will seek to engage underrepresented groups and those disproportionately impacted by the disease under study. MSD will support clinical trial investigators to enroll underrepresented groups and expand access to those who will ultimately use the products under investigation.

### **3. Site Monitoring/Scientific Integrity**

Investigative trial sites are monitored to assess compliance with the trial protocol and Good Clinical Practice (GCP). MSD reviews clinical data for accuracy, completeness, and consistency. Data are verified versus source documentation according to standard operating procedures. Per MSD policies and procedures, if potential fraud, scientific/research misconduct, privacy incidents/breaches or Clinical Trial-related Significant Quality Issues are reported, such matters are investigated. When necessary, appropriate corrective and/or preventative actions are defined and regulatory authorities and/or ethics review committees are notified.

### **B. Publication and Authorship**

Regardless of trial outcome, MSD commits to publish the primary and secondary results of its registered trials of marketed products in which treatment is assigned, according to the pre-specified plans for data analysis. To the extent scientifically appropriate, MSD seeks to publish the results of other analyses it conducts that are important to patients, physicians, and payers. Some early phase or pilot trials are intended to be hypothesis-generating rather than hypothesis testing; in such cases, publication of results may not be appropriate since the trial may be underpowered and the analyses complicated by statistical issues such as multiplicity.

MSD's policy on authorship is consistent with the recommendations published by the International Committee of Medical Journal Editors (ICMJE). In summary, authorship should reflect significant contribution to the design and conduct of the trial, performance or interpretation of the analysis, and/or writing of the manuscript. All named authors must be able to defend the trial results and conclusions. MSD funding of a trial will be acknowledged in publications.

## **III. Participant Protection**

### **A. Regulatory Authority and Ethics Committee Review (Institutional Review Board [IRB]/Independent Ethics Committee [IEC])**

All protocols and protocol amendments will be submitted by MSD for regulatory authority acceptance/authorization prior to implementation of the trial or amendment, in compliance with local and/or national regulations.

The protocol, protocol amendment(s), informed consent form, investigator's brochure, and other relevant trial documents must be reviewed and approved by an IRB/IEC before being implemented at each site, in compliance with local and/or national regulations. Changes to the protocol that are required urgently to eliminate an immediate hazard and to protect participant safety may be enacted in anticipation of ethics committee approval. MSD will inform regulatory authorities of such new measures to protect participant safety, in compliance with local and/or national regulations.

### **B. Safety**

The guiding principle in decision-making in clinical trials is that participant welfare is of primary importance. Potential participants will be informed of the risks and benefits of, as well as alternatives to, trial participation. At a minimum, trial designs will take into account the local standard of care.

All participation in MSD clinical trials is voluntary. Participants enter the trial only after informed consent is obtained. Participants may withdraw from an MSD trial at any time, without any influence on their access to, or receipt of, medical care that may otherwise be available to them.

**C. Confidentiality**

MSD is committed to safeguarding participant confidentiality, to the greatest extent possible, as well as all applicable data protection rights. Unless required by law, only the investigator, Sponsor (or individuals acting on behalf of MSD), ethics committee, and/or regulatory authorities will have access to confidential medical records that might identify the participant by name.

**D. Genomic Research**

Genomic research will only be conducted in accordance with a protocol and informed consent authorized by an ethics committee.

**IV. Financial Considerations**

**A. Payments to Investigators**

Clinical trials are time- and labor-intensive. It is MSD's policy to compensate investigators (or the sponsoring institution) in a fair manner for the work performed in support of MSD trials. MSD does not pay incentives to enroll participants in its trials. However, when enrollment is particularly challenging, additional payments may be made to compensate for the time spent in extra recruiting efforts.

MSD does not pay for participant referrals. However, MSD may compensate referring physicians for time spent on chart review and medical evaluation to identify potentially eligible participants.

**B. Clinical Research Funding**

Informed consent forms will disclose that the trial is sponsored by MSD, and that the investigator or sponsoring institution is being paid or provided a grant for performing the trial. However, the local ethics committee may wish to alter the wording of the disclosure statement to be consistent with financial practices at that institution. As noted above, all publications resulting from MSD trials will indicate MSD as a source of funding.

**C. Funding for Travel and Other Requests**

Funding of travel by investigators and support staff (eg, to scientific meetings, investigator meetings, etc.) will be consistent with local guidelines and practices.

**V. Investigator Commitment**

Investigators will be expected to review MSD's Code of Conduct as an appendix to the trial protocol, and in signing the protocol, agree to support these ethical and scientific standards.

**10.1.2 Financial Disclosure**

Financial disclosure requirements are outlined in the US Food and Drug Administration Regulations, Financial Disclosure by Clinical Investigators (21 CFR Part 54). It is the Sponsor's responsibility to determine, based on these regulations, whether a request for financial disclosure information is required. It is the investigator's/subinvestigator's responsibility to comply with any such request.

The investigator/subinvestigator(s) agree, if requested by the Sponsor in accordance with 21 CFR Part 54, to provide their financial interests in and/or arrangements with the Sponsor to allow for the submission of complete and accurate certification and disclosure statements.

The investigator/subinvestigator(s) further agree to provide this information on a Certification/Disclosure Form, frequently known as a financial disclosure form, provided by the Sponsor. The investigator/subinvestigator(s) also consent to the transmission of this information to the Sponsor in the United States for these purposes. This may involve the transmission of information to countries that do not have laws protecting personal data.

### **10.1.3 Data Protection**

The Sponsor will conduct this study in compliance with all applicable data protection regulations.

Participants will be assigned a unique identifier by the Sponsor. Any participant records or datasets that are transferred to the Sponsor will contain the identifier only; participant names or any information that would make the participant identifiable will not be transferred.

The participant must be informed that their personal study-related data will be used by the Sponsor in accordance with local data protection law. The level of disclosure must also be explained to the participant.

The participant must be informed that their medical records may be examined by Clinical Quality Assurance auditors or other authorized personnel appointed by the Sponsor, by appropriate IRB/IEC members, and by inspectors from regulatory authorities.

